#### **14.3. Analysis Populations**

The following analysis populations will be used in the analysis and presentation of the data.

##### **Safety Population:**

All subjects who were administered any test article excluding subjects who drop out prior to administering any test article. At least one observation for safety endpoints should be recorded (e.g. slit lamp findings, ocular symptoms, etc.).

##### **Intent-to-Treat (ITT) Population:**

All randomized subjects regardless of actual treatment and subsequent withdrawal from study or deviation from protocol. Subject will be analyzed as per randomized treatment.

##### **Per-Protocol (PP) Population:**

All subjects who have successfully completed all visits and did not substantially deviate from the protocol as determined by the trial cohort review committee prior to database lock. Justification of excluding subjects with protocol deviations from the Per-Protocol Population set will be documented in a memo to file. Per Protocol will be the primary analysis population.

#### **14.4. Level of Statistical Significance**

All planned analysis will be conducted with an overall type I error rate of 5%. Unless otherwise specified, all statistical tests will be 2-sided.

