### **2.3. Hypotheses**

#### **Primary hypotheses:**

1. The Test eye drops will be non-inferior to the Control eye drops with respect to change in ocular comfort from baseline at 30-Day follow-up. A non-inferiority margin of -20 point ocular comfort VAS scale will be used.

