### **14.2. Sample Size Justification**

The sample size was calculated to test for non-inferiority of the Test relative to Control eye drops with respect to the ocular comfort score using VAS with a minimum power of 85% and a two-sided type I error of 0.05. Assuming a difference between the Test and Control of 20, a common standard deviation (SD) of 35, the estimated sample size for non-

inferiority was 56 per treatment group using two-sample t-test. The sample size calculation was performed using the SAS procedure PROC POWER. The common standard deviation considered was based on results from [REDACTED] in which the estimated standard deviation of change in ocular end of day comfort from baseline at 30-day in the control group was estimated to be 2.53 in a VAS scale from 0 to 10 [REDACTED]

[REDACTED] We increased the standard deviation by one unit in case more variation will be observed in the Test group. Therefore, the standard deviation used in the sample calculation was 35 in a VAS scale from 0 to 100 ( $35 = 10 * (2.5 + 1)$ ).

The plan is to enroll 150 eligible subjects (60 per arm) with a target completion of 112 (56 per arm). During the enrollment period, the subject dropout rate will be closely monitored, if unexpectedly high dropout rate is observed (>10%) in certain arm(s), the targeted total enrollment number might be increased accordingly in order to ensure a minimum of 56 subjects per group to complete the 1-month follow-up.

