#### **Hypothesis Testing:**

The null and alternative hypotheses for no difference of Test relative to Control are as follows:

$$H_0: OR = 1$$
$$H_A: OR \neq 1,$$

where  $OR$  is odds ratio of having a Grade 2 or higher corneal staining in the Test group over the Control group.

Comparison between the Test and Control will be conducted at each follow-up visit and across all visits. The test for no difference will be based on the estimated OR and corresponding 95% confidence interval from the final model. The null hypothesis will be rejected in favor of the alternative if 1 does not fall within the 95% confidence interval of OR. The corneal staining analysis will be conducted on the Safety Population.

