**Overall Quality of Vision Score:**

Overall quality of vision will be analyzed using the same statistical model described in the primary analysis. Comparisons between Test and Control will be carried using t-tests on least square mean differences of change in quality of vision from baseline at 7-Day and 30-Day follow-up. The overall quality of vision analysis will be conducted on the Per-Protocol Population.

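### Section 14.4 claims an overall 5% type I error for all planned analyses, but the text sets no multiplicity procedure for the eight to ten tests it plans; the primary test is unaffected

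*Combined protocol and SAP*

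**What the plan says.** Section 14.4 sets the error rate for the whole plan: "All planned analysis will be conducted with an overall type I error rate of 5" per cent. It adds: "Unless otherwise specified, all statistical tests will be 2-sided".

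The tests under that statement are spread over Sections 2.3, 14.5 and 14.6:

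- **Primary.** Non-inferiority of Day-30 comfort change, judged by the lower limit of a 95% interval against -20 (14.5).
- **Corneal staining, Grade 2 or higher.** "Comparison between the Test and Control will be conducted at each follow-up visit and across all visits", with rejection when the 95% interval for the odds ratio excludes 1 (14.6).
- **Reported ocular symptoms.** Analysed by the staining method (14.6).
- **Quality of vision.** "Comparisons between Test and Control will be carried using t-tests on least square mean differences", at Day 7 and Day 30 (14.6). No level or interval is stated.
- **Day-7 comfort.** Non-inferiority with the same margin, listed as the fourth secondary hypothesis in 2.3. It has no paragraph of its own in 14.6.

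Sections 14.4 to 14.10 contain no hierarchy, gatekeeping, alpha split or adjusted interval. There is no interim analysis (14.8). Section 14.1 leaves further detail to a stand-alone SAP, to be signed before database lock; that document is not in the supplied text.

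**The concern.** An overall error rate covering all planned analyses means that the chance of any false rejection among them is held at 5%. That needs either a single test or a procedure linking several. The text describes several tests and no procedure.

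Two things are at stake. A chance difference in staining, symptoms or vision could be reported as if it came from a family controlled at 5%. And because Day-7 comfort is not tied to the primary result, non-inferiority at Day 7 could be claimed after the Day-30 test has failed. The Synopsis calls the study confirmatory and says it is to support European registration, so a stated error rate will be taken at face value.

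**Working it through.** **1. The plan's own figure.** Section 14.2 gives "minimum power of 85% and a two-sided type I error of 0.05", "a common standard deviation (SD) of 35" and a distance of 20, which is the margin in 2.3 ("A non-inferiority margin of -20 point ocular comfort VAS scale will be used"). With a true difference of zero and one-sided alpha 0.025, the normal approximation is

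n = 2 × (35/20)² × (1.960 + 1.036)² ≈ 55 per arm.

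The exact two-sample t calculation gives 56 per arm (power 85.0%; 55 per arm gives 84.4%), matching "inferiority was 56 per treatment group using two-sample t-test". One-sided 0.05 would need only 45 by the normal approximation. The primary therefore runs at one-sided 2.5%, and its sample size reproduces.

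**2. Counting the tests.**

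| Endpoint | Tests | Level | Source of level |
|---|---|---|---|
| Day-30 comfort, non-inferiority | 1 | 0.025 one-sided | explicit (14.5) |
| Staining: Day 7, Day 30, across visits | 3 | 0.05 two-sided | explicit (14.6) |
| Symptoms, same method | 3 (or 1) | 0.05 two-sided | by reference to staining |
| Vision: Day 7, Day 30 | 2 | 0.05 two-sided | inferred from 14.4 |
| Day-7 comfort, non-inferiority | 1 | 0.025 one-sided | inferred from 14.4 and 14.5 |

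The total is ten. The symptom paragraph refers to symptoms at any visit, so it can also be read as one any-visit outcome; the total is then eight.

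**3. Chance of at least one false rejection under independence.** All nulls are true, with the non-inferiority nulls exactly at -20.

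- Ten tests: 1 − 0.975² × 0.95⁸ = 0.369. The upper bound under any dependence is 8 × 0.05 + 2 × 0.025 = 0.45.
- Eight tests (one symptom test): 1 − 0.975² × 0.95⁶ = 0.301.
- The eight difference tests alone (staining 3, symptoms 3, vision 2): 1 − 0.95⁸ = 0.337.
- One test per hypothesis (three difference, two non-inferiority): 1 − 0.975² × 0.95³ = 0.185.
- Primary alone: 0.025.

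**4. With correlation.** The documents give no correlations, so these are assumptions. Test statistics for four endpoints at two visits were simulated as multivariate normal (400,000 draws). Correlation was w between visits within an endpoint, b between endpoints at the same visit, and b × w across both. Each across-visit test was the standardised sum of the two visits.

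| w | b | All ten tests | Eight difference tests |
|---|---|---|---|
| 0.3 | 0 | 0.3090 | 0.2745 |
| 0.5 | 0 | 0.2918 | 0.2584 |
| 0.5 | 0.5 | 0.2515 | 0.2276 |
| 0.9 | 0 | 0.2249 | 0.1970 |
| 0.9 | 0.5 | 0.1927 | 0.1728 |

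Over w from 0.3 to 0.9 and b from 0 to 0.5, the range is about 19% to 31% for ten tests and 17% to 27% for the eight difference tests.

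**The case against.** The strongest reply has four parts.

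- **The primary is sound.** It is one test at one visit against one margin at one-sided 2.5%, with no interim look. This stands in full. A reader might infer that the trial's main conclusion or its sample size is compromised; the documents do not support that.
- **False rejections mostly run against the sponsor.** For staining, symptoms and vision, Section 2.3 hypothesises no difference, so a chance rejection contradicts the stated hypothesis. Staining and symptoms are analysed on the Safety Population, where unadjusted testing is more sensitive to harm. This lowers the practical weight. It does not make the 5% true: the tests are two-sided, so a chance difference favouring Test is also possible, and Day-7 comfort is a favourable claim.
- **37% is not a fair headline.** It needs independence, and it needs Test to be exactly 20 points worse on comfort at both visits while matching Control on everything else. If the products are truly alike, the non-inferiority nulls are false and only the difference tests can produce a type I error. This stands, which is why the ranges carry their assumptions.
- **The stand-alone SAP may set a procedure.** Possible. Section 14.1 calls Section 14 a general description, while 14.10 says the analysis will follow the sections given. What can be said is that the supplied text specifies no procedure, not that none exists.

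A reader might also infer that every test is explicitly assigned an unadjusted 95% interval. That is explicit only for the primary and staining, and reaches symptoms by reference.

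Reading the 5% as a per-test level does not rescue the sentence in 14.4, because it speaks of an overall rate for all planned analysis.

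**Conclusion.** The concern holds for the secondary family and for the wording of 14.4, and no further. As written, the plan claims an overall 5% error rate that the supplied text gives no means of delivering. Every count considered gives a rate well above 5%, from 18.5% with one independent test per hypothesis to 37% with ten independent tests. Under the assumed correlations, ten tests give about 19% to 31%. These figures assume that all nulls hold with the non-inferiority nulls at the margin, and that vision and Day-7 comfort use the levels inferred above. If the products are alike, the relevant range is that of the difference tests: about 17% to 27%, or 34% under independence, when symptoms count as three tests.

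The one substantive gap beyond wording is that the Day-7 comfort claim does not depend on the primary succeeding.

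**What to change.** Make these changes in Section 14.4, and in the stand-alone SAP before database lock unless it already sets a procedure:

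1. Limit the error statement to the Day-30 comfort test: 5% two-sided, which is 2.5% one-sided for non-inferiority.
2. Test Day-7 comfort non-inferiority only if the Day-30 test succeeds, at the same level, and give it an analysis paragraph in 14.6.
3. Report staining, symptoms and vision with nominal 95% intervals and no claim of overall error control.
4. State whether symptoms are compared at each visit and across visits, or as one any-visit outcome.

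The cost is wording, plus fewer formal secondary claims. The primary keeps its alpha, so 56 per arm does not change.

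If the sponsor prefers to keep an overall 5% claim, the nine secondary tests could follow a successful primary by Holm's method, with a first step at 0.05/9 = 0.0056. This is less attractive for staining and symptoms, because stricter levels make an apparent finding of no difference easier to reach on safety-type outcomes.

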#### **14.5. Primary Analysis**

##### **Ocular Comfort (VAS) Score:**

Ocular comfort scores will be analyzed using a linear mixed model for repeated measures to test for the difference between the Test and Control eye drops. The regression model will include treatment group (Test, Control), time (0, 7-Day and 30-Day) and group by time interaction as fixed effect factors; and investigational site as random effect. Age and gender will be included in the model when appropriate. The correlation between measurements from the same subject across time will be modeled using unstructured (UN) variance-covariance matrix. If the estimation algorithm does not converge, then a Compound Symmetry matrix (CS) will be used. The log-likelihood ratio test will be used to test for the

homogeneity between the residual covariance structures across treatment groups. The Kenward and Roger method will be used to calculate the denominator degree of freedom.

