### **2.2. Endpoints**

#### **Primary Endpoint:**

The primary endpoint in this study is change in overall ocular comfort score from baseline at 30-Day follow-up. Subjective overall ocular comfort will be assessed at baseline, 7-Day and 30-Day follow-up using a Visual Analogue Scale (VAS) with continuous scale from 0 (extremely uncomfortable) to 100 (extremely comfortable).

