#### **Hypothesis Testing:**

The null and alternative hypotheses for non-inferiority of Test relative to Control are as follows:

$$H_0: \Delta \leq -20$$
$$H_A: \Delta > -20,$$

where  $\Delta$  is the difference between treatment groups in mean change from baseline at 30-Day follow-up (Test minus Control). The non-inferiority test will be based on the least square mean change difference and corresponding 95% confidence interval from the final model. The lower bound of the 95% confidence interval will be compared to the non-inferiority margin of -20. If the lower bound is greater than -20, the null hypothesis will be rejected, and the Test will be considered non-inferior to Control. The primary analysis will be conducted on the Per-Protocol Population. As sensitivity analysis will be conducted on the ITT Population.

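### The primary comfort model leaves baseline VAS unadjusted, so the Day-30 comparison reduces to a raw change-score difference and gives up precision that baseline adjustment would provide

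*Combined protocol and SAP*

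**What the plan says.** Section 2.2 (Primary Endpoint) has the baseline measurement in hand: "Subjective overall ocular comfort will be assessed at baseline, 7-Day and 30-Day follow-up". In the Visit 1 procedures of section 7.2, the baseline VAS is step 1.8. Randomisation is step 1.15 and first instillation step 1.16.

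Section 14.5 (Ocular Comfort (VAS) Score) fits a repeated-measures mixed model with "treatment group (Test, Control), time (0, 7-Day and 30-Day) and group by time interaction as fixed effect factors" and a random effect for site. On covariates it says only: "Age and gender will be included in the model when appropriate". On covariance: "The correlation between measurements from the same subject across time will be modeled using unstructured (UN) variance-covariance matrix", with compound symmetry as the fallback. Baseline VAS is not a covariate, and the arms are not constrained to share a baseline mean.

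The hypothesis-testing part of section 14.5 defines the parameter, which "is the difference between treatment groups in mean change from baseline at 30-Day follow-up (Test minus Control"), and compares its lower 95% confidence limit with -20. The primary population is Per-Protocol: "All subjects who have successfully completed all visits and did not substantially deviate from the protocol".

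Section 14.6 carries the model over to a secondary endpoint: "Overall quality of vision will be analyzed using the same statistical model described in the primary analysis". For corneal staining, by contrast, section 14.6 does allow baseline values as covariates.

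**The concern.** Both arms are drawn from one randomised population and baseline comfort is recorded before any study drop, so any difference in baseline means among randomised subjects is chance. A model with a free baseline mean in each arm ignores this. It subtracts baseline in full (slope fixed at 1) instead of estimating how strongly baseline predicts Day 30.

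Two things follow. The interval compared with -20 is wider than the collected data require. And if one arm happens to start more comfortable, regression to the mean lowers that arm's expected change, so the contrast moves for reasons unrelated to treatment. The design offers little protection: randomisation is stratified by site only (section 5.1), and eligibility sets no comfort threshold (section 3.2).

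**Working it through.** **Inputs.** Section 14.2: SD of change 35 on the 0-100 scale, 56 completers per arm, two-sided 0.05, at least 85% power, two-sample t-test. Sections 2.3 and 14.5: margin 20. A true difference of 0 is assumed. The correlation r between baseline and Day 30 and the SDs at each visit are not given. I take r = 0.3, 0.5 and 0.7, with equal SDs at first.

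**The plan's own figure.** SE = 35 × √(2/56) = 6.61. With noncentral t on 110 degrees of freedom and noncentrality 20/6.61 = 3.02, power is 85.0%. The stated 56 per arm reproduces.

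**What the planned model estimates.** With complete data and a free mean for each arm at each time, the fitted Day-30 minus Day-0 contrast is the difference between arms in mean raw change. Site, age and gender enter as terms that do not vary over time, so they cancel from the change. Generalised least squares on one simulated complete data set (112 subjects, 7 sites) confirmed this. The planned model and the raw change comparison both gave 6.374 with SE 4.725, at each site variance tried and with or without age.

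**What adjustment would give.** Let σ be the common visit SD.

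- Variance of change: 2σ²(1 − r)
- Variance of Day 30 given baseline: σ²(1 − r²)
- Ratio: (1 − r²) / [2(1 − r)] = (1 + r)/2

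The adjusted SD is 35 × √((1 + r)/2). The half-width is 1.982 × SD × √(2/56). The last column is 56 divided by the ratio.

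| r | Variance ratio | SD | 95% half-width | Power at 56 per arm | Equivalent n per arm, planned model |
|---|---|---|---|---|---|
| planned model | 1 | 35.0 | 13.1 | 85.0% | 56 |
| 0.3 | 0.65 | 28.2 | 10.6 | 96.1% | 86 |
| 0.5 | 0.75 | 30.3 | 11.4 | 93.3% | 75 |
| 0.7 | 0.85 | 32.3 | 12.1 | 90.2% | 66 |

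A separate three-time-point calculation (visit SD 35, r = 0.5) gives SE 6.61 with free baseline means and 5.73 with a common one. (5.73/6.61)² = 0.75, as the formula says.

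**Chance imbalance.** A baseline difference D between arms shifts the expected change-score contrast by −(1 − r)D. A change SD of 35 implies a visit SD of 35/√(2(1 − r)) = 29.6, 35.0 or 45.2. One standard error of baseline difference is then 5.6, 6.6 or 8.5 points (visit SD × √(2/56)), and the shift is 3.9, 3.3 or 2.6 points in size at r = 0.3, 0.5 or 0.7. It can favour either product.

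**Unequal SDs.** With k = Day-30 SD / baseline SD, the ratio is k²(1 − r²)/(1 + k² − 2rk). For r from 0.3 to 0.7:

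- k = 0.7: 0.42 to 0.49
- k = 1: 0.65 to 0.85
- k = 1.3: 0.81 to 0.99

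**Unpadded SD.** Section 14.2 starts from an observed 2.53 on a 0-10 scale, that is 25.3 on 0-100. At that SD the planned model has 98.6% power and a half-width of 9.5 points. Adjustment would give 99.9%, 99.8% or 99.4% power, with half-widths of 7.6, 8.2 or 8.7.

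**The case against.** The strongest reply is that nothing here is invalid. Under randomisation the change-score contrast is unbiased and holds its type I error. It targets the stated parameter, and sections 14.2 and 14.5 agree with each other. Random imbalance is already counted in the change-score standard error, and the wider interval costs the sponsor power without making a false non-inferiority claim easier. All of that stands, and it places the point as one of efficiency and conditional imbalance.

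The size is also open to challenge. The SD of 35 is deliberately padded, and at 25.3 power is already near its ceiling, so the gain shows mainly in interval width. The equal-SD assumption is unsupported, and at r = 0.7 with k = 1.3 the gain almost vanishes. The r = 0.7 row implies a visit SD of 45.2, close to the maximum of about 50 on a 0-100 scale. These points limit the figures. They do not reverse the direction: with an estimated slope the variance is no higher, apart from a trivial degree-of-freedom cost.

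Per-Protocol selection happens after randomisation, so equal expected baseline means are not guaranteed in that set. This bears on which form of adjustment to use; the planned contrast is exposed to the same selection.

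Finally, section 14.1 defers detail to a stand-alone SAP, which could add the covariate. Nothing in the supplied documents does so, and section 14.10 says the analysis will follow the sections as written.

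**Conclusion.** The concern holds. As written, the primary Day-30 comparison in the Per-Protocol set is a raw change-score difference, and the mixed model adds no precision to it. This is exact for complete data. With missing visits, as in the ITT sensitivity analysis, the identity no longer holds, but the baseline means remain free.

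The stated 85% power does not depend on the change. The loss is a variance 15% to 35% of which could be removed at r = 0.7 to 0.3, given equal visit SDs. Over k = 0.7 to 1.3 the reduction runs from about 58% to 1%. The structural point is certain; the size rests on r and k, which the documents do not give. The change should be made, because it keeps the same parameter and uses a measurement already taken before randomisation.

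**What to change.** In section 14.5 and the SAP, take change from baseline at Day 7 and Day 30 as the responses. Use treatment, time, treatment-by-time, baseline VAS and baseline-by-time as fixed effects, and keep the site effect, covariance and degrees-of-freedom rules. State that baseline is the VAS at step 1.8, since the VAS is asked again at step 1.19 after the first instillation. Apply the same model to quality of vision in section 14.6, with its own baseline.

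The alternative is to keep time 0 as a response and constrain both arms to a common mean there. The covariate form is safer in the Per-Protocol set because it does not require equal baseline means among completers.

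The cost is one line of model wording, fixed before database lock. No data, visits or subjects are added, and the margin, the parameter and the sample size stay as they are.

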## **5. TEST ARTICLE ALLOCATION AND MASKING**

### **5.1. Test Article Allocation**

Subjects will be randomly assigned to either Test or Control group based on a computer-generated randomization schedule prepared before the start of the study. The randomization will be stratified by investigational site and randomly permuted blocks of 4 assignments will be used within each study site. The randomization scheme will be generated using the PROC PLAN procedure from the Statistical Analysis System (SAS) Software version 9.4 or higher

The study site will follow the randomization scheme provided and will complete enrollment according to the randomization list and will not pre-select or assign subjects. The assignment of the subjects must be performed at the first baseline visit (Visit 1). The following must have occurred prior to randomization:

- Informed consent has been obtained
- Subject meets all the inclusion / exclusion criteria
- Subject history and baseline information has been collected

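### The site, age and gender terms in the primary comfort model cancel out of the Day-30 change contrast, so the Per-Protocol non-inferiority test does not use the randomization stratum

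*Combined protocol and SAP*

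**What the plan says.** Section 5.1 makes site the stratification factor: "The randomization will be stratified by investigational site and randomly permuted blocks of 4 assignments will be used within each study site".

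Section 14.5 sets out the primary model: "Ocular comfort scores will be analyzed using a linear mixed model for repeated measures". The response is the score itself at each visit, and baseline is one of the three levels of time. The fixed part is treatment, time and their interaction; the rest reads "group by time interaction as fixed effect factors; and investigational site as random effect". On covariates: "Age and gender will be included in the model when appropriate". The within-subject correlation is "modeled using unstructured (UN) variance-covariance matrix", with compound symmetry as the fallback. No interaction of site, age or gender with time is named.

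Under Hypothesis Testing in 14.5, the parameter is the Test minus Control difference in mean change from baseline at Day 30, and "The non-inferiority test will be based on the least square mean change difference and corresponding 95% confidence interval from the final model". The lower limit is compared with -20. The Per-Protocol Population, defined in 14.3 as requiring completion of all visits, is primary; ITT is a sensitivity analysis.

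Section 14.6 carries the model over: "Overall quality of vision will be analyzed using the same statistical model described in the primary analysis". Section 14.1 defers further detail to a stand-alone SAP, which is not among the documents.

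**The concern.** Someone reading 14.5 would take the non-inferiority test to be adjusted for site, and for age and gender where used. A term that adds the same amount to a subject's score at every visit cannot affect a contrast between two visits.

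Blocking within site balances the arms on anything that differs between sites, including how much comfort changes over the month. That balance reduces the true sampling error of the treatment difference. An analysis with no site effect on change leaves the between-site part of the variance in its residual, so its standard error does not reflect the gain. At stake is the width of the interval for the primary test and, by the same mechanism, for quality of vision.

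**Working it through.** **Inputs.** From 14.2: margin 20, SD of change 35, 56 completers per arm, power 85%, two-sided alpha 0.05. From 4.3: up to 7 sites, at least 16 subjects per site (7 x 16 = 112). Assumed, because the documents give no figure: the share r of the variance of change that lies between sites, taken from 0 to 20%.

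**Plan's own figure.** The normal approximation n = 2(1.960 + 1.036)² x 35² / 20² gives 55 per arm. The exact noncentral-t calculation gives 56 per arm with power 0.850. The plan's 56 is reproduced, and it assumes no site adjustment.

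**Cancellation.** Write the score of subject i in arm g at time t as m(g,t) + c(i) + error, where c(i) collects the site effect and any age and gender effects and does not depend on t. With a separate mean for each arm and visit and complete data, the estimating equations give fitted m(g,t) = raw mean(g,t) - average fitted c in arm g. The subtracted amount is the same at every t, so fitted m(g,30) - m(g,0) is the raw mean change in arm g. The treatment contrast is therefore the raw difference in mean change, and the site variance does not enter its variance.

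**Numerical check.** One artificial complete dataset had 112 subjects in 7 sites and 3 visits, with the covariance matrix held fixed. The raw difference in mean change was -7.458, SE 8.228.

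| Model | Contrast | SE |
|---|---|---|
| No site, no covariates | -7.458 | 8.228 |
| Random site, variance 225 | -7.458 | 8.228 |
| Random site (225 or 5000) + age + gender | -7.458 | 8.228 |
| Fixed site main effects + age + gender | -7.458 | 8.228 |
| Fixed site-by-time + age + gender | -3.913 | 8.399 |

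Only site-by-time acts on the contrast. The size of that last shift should not be read as typical: arms in this dataset were not balanced within site, and a fixed covariance matrix cannot show any fall in residual variance. Under compound symmetry the contrast was again -7.458, and its SE (6.547) did not change when site, age and gender were added. A second dataset gave 8.204 (SE 5.669) with no site term, with site variance 225, and with age plus site variance 225 or 5000. With the covariance estimated by REML in 16 simulated datasets, the stated model matched the raw change comparison to two decimals in all 16.

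With about 7% of Day-30 values missing, as in an ITT set, the contrast was -8.73 without the terms and -8.44 with them; the SE was 8.260 and 8.261. The cancellation is then close but not exact.

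**Size by formula.** Half-width without site: t(0.975, 110) x 35 x sqrt(2/56) = 13.11. With site acting on change, error df = 112 - 8 = 104, and the half-width is t(0.975, 104) x 35 x sqrt(1 - r) x sqrt(2/56):

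- r = 0: 13.12
- r = 5%: 12.78
- r = 10%: 12.44
- r = 20%: 11.73

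Simulated average half-widths, as written against site-adjusted, were 13.07 v 13.07 at 0%, 13.03 v 12.75 at 5% and 12.99 v 12.42 at 10%.

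**Power and error.** These come from 20,000 simulated trials per setting, with 7 sites of 16 and arms balanced within site. Power is at a true difference of 0, and one-sided error at a true difference of -20.

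| r | Power as written | Power with site | Error as written | Error with site |
|---|---|---|---|---|
| 0 | 84.8% | 84.8% | 0.024 | 0.024 |
| 5% | 85.9% | 86.8% | 0.022 | 0.025 |
| 10% | 86.6% | 88.5% | 0.019 | 0.024 |
| 20% | 87.5% | 91.3% | 0.016 | 0.025 |

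The simulation error on a power near 85% is about 0.25 points (sqrt(0.85 x 0.15 / 20,000)), so the first row agrees with the planned 85.0%. Power as written rises with r because stratification makes the estimate itself more precise, even though the model does not credit it.

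**The case against.** The strongest reply is that little follows from the algebra. Because the contrast is a within-subject change, every site difference in comfort level has already gone. What remains depends on a between-site share that the documents do not give. The sample size was computed for an unadjusted t-test, so no planned power is lost. The SD of 35 is itself raised from an observed 2.53 on a 0-10 scale; at 25.3, power with 56 per arm is 98.6%, so the gain may have no practical effect on the decision. All of this stands.

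Nor is the gain certain in a given trial. In 6,000 simulated trials per setting with randomly unequal sites, 120 randomized and 112 completing, power as written against site-adjusted was 85.3% v 85.0% at 0%, 85.3% v 86.1% at 5% and 86.7% v 88.2% at 10%. The adjusted interval was the wider one in 66%, 29% and 13% of trials respectively. This also stands, though the losses at 0% are trivial on average.

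Two further points limit the scope. A single intercept per site is the natural reading of 14.5 but is not spelled out, and the stand-alone SAP might say more. No size can be given for quality of vision, because the documents state no SD for it; only the cancellation carries over.

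A reader might go further and infer that the non-inferiority test is invalid, that the interval is certainly too wide, or that the trial is underpowered. The documents support none of these. Simulated error does not exceed 0.025, excess width needs sites to differ in change, and the 85% target is reached without any site adjustment.

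**Conclusion.** The point holds as one of efficiency and clarity. As 14.5 is written, the site, age and gender terms have no effect on the primary Per-Protocol contrast, and the test does not use the factor by which the trial randomizes. In the ITT sensitivity analysis the terms have almost no effect.

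The size rests on the assumed between-site share of the variance of change: about 0.3 VAS points of half-width at 5% and 0.6 at 10%, against a margin of 20, and roughly 1 and 2 points of power. At 0% there is no gain, or a negligible loss. The error is in the conservative direction. The conclusion assumes that site enters as one effect constant over visits and that age and gender, if used, enter as main effects.

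**What to change.** In 14.5, and in the stand-alone SAP before database lock, replace the random site term with site and site-by-time as fixed effects. Equivalently, analyze the Day-30 change with site as a fixed factor. If age and gender are kept, include their interactions with time, since as main effects they do nothing to this contrast. Carry the same specification to quality of vision in 14.6.

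The cost is a change of wording and, with 7 sites, about 6 error degrees of freedom (104 instead of 110). If sites do not differ in change, the half-width by formula goes from 13.11 to 13.12. The sample size does not need to change.
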